### **5.3. Analysis Populations**

#### **5.3.1. Full Analysis Set**

The FAS includes all subjects enrolled in the study who received at least 1 dose of INCAGN01876, nivolumab, or ipilimumab. The FAS will be used for the summary of demographics, baseline characteristics, subject disposition, safety, study treatment administration, and analyses of all efficacy data.

- **Phase 1 FAS Population**

The Phase 1 FAS population includes all subjects in the FAS population who are enrolled in the Phase 1 portion of the study and received at least 1 dose of INCAGN01876, nivolumab, or ipilimumab.

- **Phase 1 FAS INCAGN01876 Population**

The Phase 1 FAS population includes all subjects in the FAS population who are enrolled in the Phase 1 portion of the study and received at least 1 dose of INCAGN01876.

- **Phase 1 FAS Weighted Nivolumab Population**

The Phase 1 FAS weighted nivolumab population includes all subjects in the FAS population who are enrolled in the Phase 1 portion of the study and received at least 1 dose of nivolumab administered in mg/kg. This includes subjects enrolled into Treatment Groups D and E.

- **Phase 1 FAS Fixed Nivolumab Population**

The Phase 1 FAS fixed nivolumab population includes all subjects in the FAS population who are enrolled in the Phase 1 portion of the study and received at least 1 dose of nivolumab administered in mg. This includes subjects enrolled into Treatment Groups A and B.

- **Phase 1 FAS Ipilimumab Population**

The Phase 1 FAS ipilimumab population includes all subjects in the FAS population who are enrolled in the Phase 1 portion of the study and received at least 1 dose of ipilimumab.

- **Phase 2 FAS Population**

The Phase 2 FAS population includes all subjects in the FAS population enrolled in Phase 2 of the study who received at least 1 dose of INCAGN01876, nivolumab, or ipilimumab.

Specific analysis populations to be used for evaluating the Simon 2-stage efficacy rules include the following subgroups:

- Treatment Group F adenocarcinoma of the endometrium
- Treatment Group F with gastric cancer
- Treatment Group F with SCCHN cancer
- Treatment Group G with adenocarcinoma of the endometrium
- Treatment Group G with gastric cancer
- Treatment Group G with SCCHN cancer
- Treatment Group H with adenocarcinoma of the endometrium
- Treatment Group H with gastric cancer
- Treatment Group H with SCCHN cancer
- Treatment Group J with adenocarcinoma of the endometrium
- Treatment Group J with gastric cancer
- Treatment Group J with SCCHN cancer

- Treatment Group K with adenocarcinoma of the endometrium
- Treatment Group K with gastric cancer
- Treatment Group K with SCCHN cancer
- Treatment Group L with adenocarcinoma of the endometrium
- Treatment Group L with gastric cancer
- Treatment Group L with SCCHN cancer

Table summaries, unless otherwise indicated, will be provided by treatment group and tumor type-specific cohort.

- **Phase 2 FAS INCAGN01876 Population**

The Phase 2 FAS population includes all subjects in the FAS population who are enrolled in the Phase 2 portion of the study and received at least 1 dose of INCAGN01876.

- **Phase 2 FAS Weighted Nivolumab Population**

The Phase 2 FAS weighted nivolumab population includes all subjects in the FAS population who are enrolled in the Phase 2 portion of the study and received at least 1 dose of nivolumab administered in mg/kg. This includes subjects enrolled into Treatment Groups J, K, and L.

- **Phase 2 FAS Fixed Nivolumab Population**

The Phase 2 fixed FAS nivolumab population includes all subjects in the FAS population who are enrolled in the Phase 2 portion of the study and received at least 1 dose of nivolumab administered in mg. This includes subjects enrolled into Treatment Groups F, G, and H.

- **Phase 2 FAS Ipilimumab Population**

The Phase 2 FAS ipilimumab population includes all subjects enrolled in the Phase 2 portion of the study who received at least 1 dose of ipilimumab.

### **5.3.2. Response Evaluable Populations**

#### **5.3.2.1. Phase 1 Response Evaluable Population**

The Phase 1 response evaluable population includes all subjects enrolled in Phase 1 of the study who have received at least 1 dose of INCAGN01876, nivolumab, or ipilimumab; completed a baseline scan; and met at least 1 of the following criteria:

- $\geq 1$  postbaseline scan OR
- The subject has been on the study for a minimum of 64 days of follow-up OR
- The subject has discontinued from treatment.

### 5.3.2.2. Phase 2 Response Evaluable Population

The Phase 2 response evaluable population includes all subjects enrolled in Phase 2 of the study who have received at least 1 dose of INCAGN01876, nivolumab, or ipilimumab; completed a baseline scan; and met at least 1 of the following criteria:

- $\geq 1$  postbaseline scan OR
- The subject has been on the study for a minimum of 64 days of follow-up OR
- The subject has discontinued from treatment.

[REDACTED]

[REDACTED]

[REDACTED]

[REDACTED]

[REDACTED]

[REDACTED]

[REDACTED]

[REDACTED]

[REDACTED]

## **6. BASELINE, EXPOSURE, AND DISPOSITION VARIABLES AND ANALYSES**

[Appendix A](#) provides a list of data displays. Sample data displays will be provided in a separate document.

### **6.1. Baseline and Demographics, Physical Characteristics, and Disease History**

#### **6.1.1. Demographics**

The following demographics will be summarized for the Phase 1 FAS population by treatment group and dose level and for the Phase 2 FAS population by treatment group and tumor type: age, sex, race, ethnicity, and ECOG performance status.

#### **6.1.2. Baseline Disease Characteristics and Disease History**

For each type of tumor, primary tumor histology, time from initial diagnosis in months, stage at initial diagnosis, current stage of disease, current site of disease, and tumor markers will be summarized for all subjects in the Phase 1 FAS population by treatment group and dose level and Phase 2 FAS population by treatment group and tumor type.

#### **6.1.3. Prior Therapy**

Number of prior systemic cancer therapy regimens will be summarized for all subjects in the Phase 1 FAS population by treatment group and dose level and Phase 2 FAS population by treatment group and tumor type. Regimen name, component drugs, start and stop date, purpose of the regimen, best response, reason for discontinuation, and date of relapse/progression will be listed by total number and by number of prior systemic cancer therapies taken for both advanced and metastatic disease.

Number of subjects who received prior radiation will be summarized for the FAS population. Radiotherapy type, body site, start and stop date, total dose, and best response will be listed.

Number of subjects who had prior surgery or surgical procedure for the malignancies under study will be summarized for the FAS population. Date and description of the surgery/procedure will be listed.

Number of subjects with prior immunotherapy and prior anti-PD-1/PD-L1 therapy will be summarized for the Phase 1 FAS population by treatment group and dose level and the Phase 2 FAS population by treatment group and tumor type. Prior immunotherapy type, start and stop date, total dose, and best response will be listed.

#### **6.1.4. Medical History**

Medical history will be summarized according to assigned treatment group by dose level for subjects in the Phase 1 FAS population and by tumor type for the Phase 2 FAS population. This summation will include the number and percentage of subjects with significant medical history for each body system/organ class as documented on the CRF.

## 6.2. Disposition of Subjects

The number and percentage of subjects who were enrolled, treated, completed the study, discontinued study treatment with a primary reason for discontinuation, and discontinued from the study with a primary reason for withdrawal will be summarized for the Phase 1 FAS population by treatment group and dose level and for the Phase 2 population by treatment group and tumor type. The number of subjects enrolled by site will also be provided by treatment group.

## 6.3. Protocol Deviations and Violations

Protocol deviations and violations recorded on the CRF will be presented in the subject data listings.

## 6.4. Exposure

### 6.4.1. Exposure for INCAGN01876

For subjects in the FAS population, exposure to INCAGN01876 will be summarized descriptively as the following:

- **Total number of infusions:** Total number of infusions per subject with a nonzero dose of INCAGN01876.
- **Dose administered per cycle (mg/kg):** The actual dose administered in mg/kg per cycle.
- **Total dose administered (mg/kg):** The total cumulative, actual dose administered (in mg/kg) across cycles for each subject will be determined according to the following calculation:
  - For an infusion  $i$ , let  $C_i$  be the concentration (in mg/mL) of INCAGN01876 and  $V_i$  be the total volume administered (in mL) reported on the INCAGN01876 dosing CRF; let  $W$  be the subject's baseline weight (in kg), and  $N$  be the total number of infusions:
$$\text{Total dose administered (in mg/kg)} = \sum_{i=1}^N \frac{C_i \times V_i}{W}.$$
- **Average dose of INCAGN01876 (mg/kg):** The average dose (mg/kg) will be the total dose administered (in mg/kg) divided by the total number of infusions.
- **Dose administered per cycle (mg):** The actual dose administered in mg per cycle.
- **Total dose administered (mg):** Total cumulative, actual dose administered (in mg) across cycles for each subject will be determined according to the following calculation:
  - For an infusion  $i$ , let  $C_i$ ,  $V_i$ , and  $N$  be defined as above:
$$\text{Total dose administered (in mg)} = \sum_{i=1}^N C_i \times V_i.$$
- **Average dose of INCAGN01876 (mg):** The average dose (mg) will be the total dose administered (in mg) divided by the total number of infusions.

#### 6.4.2. Exposure for Nivolumab

For subjects in the Phase 1 FAS population by treatment group and dose level and the Phase 2 FAS population by treatment group and tumor type, exposure to nivolumab will be summarized descriptively as the following:

- **Total number of infusions:** Number of infusions of nivolumab (mg) for a subject will be the number of administered, nonzero infusions of nivolumab (mg) recorded on the Nivolumab Dosing CRF.
- **Dose administered per cycle of nivolumab (mg):** The actual dose administered in mg per cycle. Dose administered per cycle of nivolumab (mg) will only be summarized for subjects in the Phase 1 FAS Fixed Nivolumab Population and Phase 2 FAS Fixed Nivolumab Population.
- **Average dose of nivolumab (mg):** The average dose of nivolumab (mg) will be the sum of the doses of nivolumab recorded (mg) on the Nivolumab Dosing CRF divided by the number of infusions of nivolumab (mg). Average dose of nivolumab (mg) will only be summarized for subjects in the Phase 1 FAS Fixed Nivolumab Population and Phase 2 FAS Fixed Nivolumab Population.
- **Dose administered per cycle of nivolumab (mg/kg):** The actual dose administered in mg/kg per cycle. Dose administered per cycle of nivolumab (mg/kg) will only be summarized for subjects in the Phase 1 FAS Weighted Nivolumab Population and Phase 2 FAS Weighted Nivolumab Population.
- **Average dose of nivolumab (mg/kg):** The average dose of nivolumab (mg/kg) will be the sum of the doses of nivolumab recorded (mg/kg) on the Nivolumab Dosing CRF divided by the number of infusions of nivolumab (mg/kg). Average dose of nivolumab (mg/kg) will only be summarized for subjects in the Phase 1 FAS Weighted Nivolumab Population and Phase 2 FAS Weighted Nivolumab Population.

#### 6.4.3. Exposure for Ipilimumab

- **Total number of infusions:** Number of doses of ipilimumab for a subject will be the number of administered, nonzero infusions of ipilimumab recorded on the Ipilimumab Dosing CRF.
- **Dose administered per cycle of ipilimumab (mg/kg):** The actual dose administered in mg/kg per cycle.
- **Average dose of ipilimumab (mg/kg):** The average dose of ipilimumab (mg/kg) will be the sum of the doses of ipilimumab recorded on the Ipilimumab Dosing CRF divided by the number of infusions of ipilimumab.

## **6.5. Prior and Concomitant Medication**

Prior medications and concomitant medications will be coded using the WHO Drug Dictionary March 2017 version and summarized by WHO drug class and WHO drug term by treatment group and dose level in the Phase 1 FAS population and by treatment group and tumor type in the Phase 2 FAS population. Results will be summarized as number and percentage of subjects with prior and concomitant medications by preferred term and WHO drug class.

## **7. EFFICACY**

Sample data displays are provided in a separate document.

### **7.1. General Considerations**

The primary efficacy endpoint for this study is ORR per RECIST v1.1 assessed in the Phase 2 Response Evaluable Population. Secondary efficacy endpoints of this study include ORR, DOR, duration of disease control, DCR, and PFS by investigator assessment based on RECIST v1.1 and mRECIST v1.1 as well as OS assessed at 1 year and 2 years.

### **7.2. Efficacy Hypotheses**

Each Simon 2-stage design will test the null hypothesis that the true ORR is less than or equal to the clinically insignificant response rate  $p_0$  against the alternative hypothesis that the true ORR is equal to the target rate of  $p_1$ . For each Simon 2-stage design, the value for  $p_0$  is determined by a historical response rate. The same values for  $p_0$  and  $p_1$  will be used for alternative dosing sequences in the same tumor type and treatment combination. For example, the gastric cohorts in Treatment Groups F, G, and H will all use the same value for  $p_0$  and  $p_1$ .

### **7.3. Analysis of the Primary and Secondary Efficacy Parameters**

#### **7.3.1. Response Criteria**

Overall disease status will be categorized using RECIST v1.1 and mRECIST v1.1. Subjects will have their overall response evaluated as CR, PR, SD, PD, or NE at each postbaseline radiological assessment based on changes in target lesions, nontarget lesions, and appearance of new lesions.

#### **7.3.2. Objective Response Rate and Best Overall Response**

##### **7.3.2.1. Confirmed ORR and Confirmed BOR by RECIST v1.1**

Per RECIST v1.1, in nonrandomized studies where response is the primary endpoint, confirmation of PR and CR is required to ensure responses are not the result of measurement error. Therefore, a subject is defined as a confirmed objective responder if the subject has an overall response of CR or PR at any postbaseline visit that is confirmed at a subsequent timepoint at least 4 weeks later, before the first occurrence of PD. Confirmed objective responders will be assessed based on RECIST v1.1.

Confirmed ORR is defined as the proportion of subjects with confirmed overall responses. Confirmed ORR will be estimated with 95% CIs. Confidence intervals will be based on the method for Simon 2-stage CIs of response rates outlined in Koyama and Chen (2008).

Confirmed ORR will be summarized by treatment group and tumor type as primary endpoint for the Phase 2 response evaluable population.

In general, confirmed BOR is the best response recorded postbaseline before and including the first PD, in the order of CR, PR, SD, PD and NE, in which CR and PR must be confirmed at a subsequent timepoint at least 4 weeks after the CR or PR is observed. Responses of CR, PR, or SD after the first assessment of PD will not be considered. In the case of SD, measurements must meet the SD criteria at least once after the date of first dose at a minimum interval of 49 (56 – 7) days. Subjects who fail to meet this criterion will have confirmed BOR of PD if the next available assessment indicates PD or NE if there is no additional assessment available.

Under RECIST v1.1, if radiologic imaging shows CR or PR, a tumor assessment should be repeated at a minimum of 4 weeks to confirm the response in order to claim the CR or PR as the confirmed BOR. If there is no second CR or PR tumor assessment, the CR or PR will be unconfirmed. Table 4 lists the scenarios of responses that can occur after an unconfirmed CR or PR and provides a rule for determining the confirmed BOR in each scenario. A sensitivity analysis for the ORR, in which BOR is determined using unconfirmed PR and CR, is detailed in Section 7.3.2.2.

For determination of confirmed BOR, confirmatory scans with a response of NE will be subsequently followed by another scan at a minimum of 4 weeks. For example, in the case of PR at the first timepoint followed by NE at a subsequent timepoint, if a third scan shows a PR, then the confirmed BOR will be PR. There will be no third confirmatory scans performed for a loss of response. For example, if a response of PR at the first timepoint is followed by a response of SD or PD at a subsequent timepoint, the confirmed BOR will be determined using the rules in Table 4.

**Table 4: Derivation of Confirmed Best Overall Response**

Overall Response at First Timepoint	Overall Response at Subsequent Timepoint	Confirmed Best Overall Response
CR	CR	CR
CR	PR	SD, PD, or PR a
CR	SD	SD provided minimum criteria for SD duration met, otherwise, PD
CR	PD	SD provided minimum criteria for SD duration met, otherwise, PD
CR	NE	SD provided minimum criteria for SD duration met, otherwise NE
PR	CR	PR
PR	PR	PR
PR	SD	SD
PR	PD	SD provided minimum criteria for SD duration met, otherwise, PD
PR	NE	SD provided minimum criteria for SD duration met, otherwise NE
NE	NE	NE

a If a CR is truly met at the first timepoint, then any disease seen at a subsequent timepoint, even disease meeting PR criteria relative to baseline, makes the disease status PD at that point (since disease must have reappeared after CR). Confirmed BOR would depend on whether the minimum duration for SD was met. However, sometimes CR may be claimed when subsequent scans suggest small lesions were likely still present and in fact the subject had a PR, not a CR at the first timepoint. Under these circumstances, the original CR should be changed to a PR, and the confirmed BOR is PR.

For subjects with measurable disease at baseline, the RECIST v1.1 assessment criteria presented in [Table 5](#) can be used to determine the overall disease status at a given timepoint based on the target lesion, nontarget lesion, and new lesion assessment.

**Table 5: RECIST Evaluation Criteria for Overall Response: Measurable Disease at Baseline**

Target Lesions	Nontarget Lesions	New Lesions	Overall Response
CR	CR	No	CR
CR	Non-CR/non-PD	No	PR
CR	NE	No	PR
PR	Non-PD or NE	No	PR
SD	Non-PD or NE	No	SD
Not all evaluated	Non-PD	No	NE
PD	Any	Yes or No	PD
Any	PD	Yes or No	PD
Any	Any	Yes	PD

**7.3.2.1.1. Subgroup Analyses for Confirmed Best Overall Response Under RECIST v1.1 in Phase 2**

Subgroups will be formed based on the following subject characteristics and baseline variables for those subjects enrolled in Phase 2 of the study whose data are available.

- PD-L1 expression within tumor type: high, negative/low, unknown
- Number of prior therapies for advanced and metastatic disease within tumor type
- Subjects with > 1 postbaseline scan within tumor type
- Tumor-type disease characteristics including the following:
  - Endometrium – MSI status (high, low, stable, unknown)
  - SCCHN – human papilloma virus status (positive vs negative)

**7.3.2.2. Unconfirmed ORR and Unconfirmed BOR by RECIST v1.1 – Sensitivity and Supportive Analyses for Confirmed ORR and Confirmed BOR by RECIST v1.1**

A sensitivity analysis for the ORR assessed under RECIST v1.1 will be performed using unconfirmed CRs and PRs. The unconfirmed BOR is defined as the best response recorded postbaseline prior to and including the first PD, in the order of CR, PR, SD, PD, and NE. For this definition, responses of CR and PR do not need to be confirmed at a subsequent timepoint. In the case of SD, measurements must meet the SD criteria at least once after the date of first dose at a minimum interval of 49 (56 – 7) days. Subjects who fail to meet this criterion will have BOR of PD if the next available assessment indicates PD or NE if there is no additional assessment available.

Unconfirmed ORR will be summarized by treatment group and tumor type as a sensitivity analysis for the primary endpoint ORR for the Phase 2 Response Evaluable Population and as a sensitivity analysis for the secondary endpoint ORR for the Phase 1 Response Evaluable Population.

### 7.3.2.2.1. Subgroup Analyses for Unconfirmed Best Overall Response by RECIST v1.1 in Phase 1

For the sensitivity analysis for unconfirmed BOR, subgroups will be formed based on the following subject characteristics and baseline variables for those subjects enrolled in Phase 1 of the study whose data are available.

- Prior treatment with an anti-PD-1/PD-L1 therapy within tumor type: Yes/No

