- ^l On-study imaging will be performed at Week 8 and then every 8 weeks (± 7 days) for the first 12 months and then every 12 weeks (± 7 days) thereafter. Imaging should follow calendar days starting with Day 1 of INCAGN01876 treatment and should NOT be adjusted for delays in cycle starts. If imaging shows disease progression, then another imaging assessment should be performed at a minimum of 4 weeks but no later than 6 weeks later to confirm progression per mRECIST.
- ^m If scan was obtained within 4 weeks before the date of discontinuation, then a scan at treatment discontinuation (EOT) is not mandatory. For subjects who discontinue study therapy without confirmed disease progression, a radiologic evaluation should be repeated at the time of treatment discontinuation (ie, date of discontinuation ± 4 week window).
- ⁿ For subjects who discontinue treatment for reasons other than disease progression, every effort should be made to continue monitoring their disease status every 8 weeks (± 7 days) by radiographic imaging until 1) start of new anticancer therapy, 2) documented disease progression, 3) death, 4) the end of the study, or 5) withdrawal of consent, whichever occurs first.
- Note:** As of Protocol Amendment 5, no further disease status follow-up assessments will be required beyond the last safety follow-up visit.

Table 11: Schedule of Laboratory Assessments

Visit Day (Range)	Protocol Section	Timing of Assessment	Screening Day -28 to -1	Treatment										Post-Treatment			
				C1		C2	C3	C4	C6		C7	Every 4th Cycle (C8, C12)	All Other Cycles	EOT	Safety Follow-Up Visit 1	Safety Follow-Up Visit 2	
				D1	D8	D1	D1	D1	D1	D8	D1	D1	D1				
Evaluation/Window					± 1 day	± 3 days	± 3 days	± 3 days	± 3 days	± 3 days	± 3 days	± 3 days	± 3 days	± 3 days	± 3 days	30 days (+ 7 days)	60 days (+ 7 days)
Local laboratory tests^a																	
Comprehensive serum chemistries ^b	7.6.5	N/A	X ^c	X ^d	X	X	X	X	X	X	X	X	X	X	X	X	X
Hematology with differential	7.6.5	N/A	X ^c	X ^d	X	X	X	X	X	X	X	X	X	X	X	X	X
Coagulation panel ^e	7.6.5	N/A	X ^c														
Urinalysis	7.6.5	N/A	X ^c											X			
Endocrine function tests	7.6.5	N/A	X ^c					X					X	X			
Hepatitis B and C	7.6.5.2	N/A	X														
Serum pregnancy test (childbearing females only) ^f	7.6.5.1	N/A	X											X			
Urine pregnancy test (childbearing females only)	7.6.5.1	N/A			X ^g												

- ^a All safety laboratory assessments will be performed locally.

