In order to determine whether the target response rate ( $p_1$ ) is likely, an initial number of evaluable subjects ( $n_1$  subjects) treated at the MTD or PAD and schedule of INCAGN01876 within the corresponding doublet or triplet expansion cohort will be enrolled in a cohort (Stage 1). If there are  $r_1$  or fewer responses in the cohort, it will be concluded that the true response rate is unlikely to be greater than or equal to the target rate, and no more subjects will be enrolled in that tumor type in Stage 2. In the cohorts in which greater than  $r_1$  responses are observed among the Stage 1 subjects,  $n_2$  additional evaluable subjects will be treated in Stage 2 to estimate the response rate. At the end of Stage 2, if  $\leq r$  subjects have responded among the  $n$  evaluable subjects, the doublet or triplet schedule will be declared nonpromising for that cohort. In other words, after the study is finished, if there is a sufficient number of responses in the 2 stages combined, the study doublet or triplet is considered promising; otherwise it is considered nonpromising. The detailed calculations for each tumor type-specific doublet and triplet cohort are based on a 1-sided Type I error of 0.05 and power of 85%. The individual  $p_0$  and  $p_1$  values for the tumor types within doublet or triplet expansion cohorts are listed in [Table 2](#). [Table 2](#) shows that there are 4 unique Simon 2-Stage designs: the Simon 2-stage designs for gastric and SCCHN within the INCAGN01876 + nivolumab cohorts use the same assumptions as the Simon 2-stage designs for gastric and SCCHN within the INCAGN01876 + nivolumab + ipilimumab cohorts. [Figure 2](#) shows the power to reject the null hypothesis under various response rates for the 4 unique Simon 2-stage designs, in which each line of the figure represents the power for a unique Simon 2-stage design.

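### The planned subgroup of subjects with more than one postbaseline scan is selected on outcome, so its confirmed response rate can only equal or exceed the full-denominator rate

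*SAP*

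**What the plan says.** SAP 7.3.2.1.1 introduces its list with "Subgroups will be formed based on the following subject characteristics and baseline variables". Most entries fit that description: PD-L1 expression, number of prior therapies, and tumor-specific markers. One entry is "Subjects with > 1 postbaseline scan within tumor type". The section gives no rationale, caveat or landmark time for it.

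SAP 7.3.2.1 defines a confirmed objective responder as a subject whose CR or PR is "confirmed at a subsequent timepoint at least 4 weeks later, before the first occurrence of PD". It adds: "If there is no second CR or PR tumor assessment, the CR or PR will be unconfirmed". In SAP Table 4, every row that ends in a confirmed CR or PR uses two timepoints.

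The primary analysis is tied to a wider set: "Confirmed ORR will be summarized by treatment group and tumor type as primary endpoint for the Phase 2 response evaluable population". Under SAP 5.3.2.2, a treated subject with a baseline scan enters that population through any one of three routes: at least one postbaseline scan, 64 days on study, or "The subject has discontinued from treatment". Subjects with no postbaseline scan or only one can therefore be in the primary denominator.

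On imaging, the notes to Protocol Table 10 state "On-study imaging will be performed at Week 8 and then every 8 weeks". A repeat scan is due 4 to 6 weeks after a scan that shows progression. Protocol Table 13 leaves that repeat scan to the physician when the subject is clinically unstable.

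**The concern.** A subgroup should be defined by something fixed before treatment, so that belonging to it does not depend on what happened afterwards. This one depends on remaining under imaging long enough to be scanned twice, which is also a condition for being a confirmed responder. Selection and endpoint therefore overlap: the restriction leaves the numerator untouched and shrinks the denominator.

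It also undoes a protection that the SAP provides elsewhere. The response evaluable population deliberately keeps subjects who stopped early without an adequate scan and counts them as nonresponders. The subgroup takes them out again.

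At stake is a confirmed response rate, presented as an ordinary baseline subgroup, that looks better than the primary result solely because of how its members were chosen.

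**Working it through.** **Plan's own figure.** The SAP gives no number for this subgroup, so there is none to reproduce. The cohort size used below, 46, is that of the SCCHN and gastric doublet designs in SAP Table 2 (r1/n1 = 3/16, r/n = 10/46). To check that this design was read correctly: the binomial probability of 3 or fewer responses in 16, at true rates of 15, 20, 25, 30 and 35%, is 79.0, 59.8, 40.5, 24.6 and 13.4%. This matches SAP Table 11.

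**Step 1: who is in the subgroup.** More than one scan means at least two. A confirmed CR or PR needs a first assessment and a later one, so at least two. All confirmed responders are in.

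**Step 2: who is out.** A subject with 0 or 1 postbaseline scan cannot have a confirmed response. A single-scan CR or PR is unconfirmed and counts as a nonresponse for this endpoint. Everyone removed is a nonresponder. If the complementary group were tabulated, its confirmed rate would be zero by construction.

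**Step 3: effect on the rate.** Let R be the confirmed responders, N the response evaluable subjects in the cohort, m those with 0 or 1 postbaseline scan, and f = m/N.

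- Full denominator: R/N.
- Subgroup: R/(N − m) = (R/N) × 1/(1 − f).
- Relative inflation: 1/(1 − f) − 1, which is 0 only if m = 0. If R = 0, both rates are 0.

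**Step 4: size.** The documents do not give f, so 10% to 40% is an assumed range. The count of 9 responders in 46 (19.6%) is also only illustrative.

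| Assumed f | 1/(1 − f) − 1 | m, rounded, of 46 | Subgroup rate |
|---|---|---|---|
| 10% | 11% | 5 | 9/41 = 22.0% |
| 20% | 25% | 9 | 9/37 = 24.3% |
| 30% | 43% | 14 | 9/32 = 28.1% |
| 40% | 67% | 18 | 9/28 = 32.1% |

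Because m is rounded to whole subjects, the example rows differ slightly from the second column; the last row, for instance, gives 46/28 − 1 = 64%.

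**Step 5: who is likely to be removed.** With scans at Week 8 and every 8 weeks after that, the removed subjects are mainly those who die before a second scan, those who progress while clinically unstable and are not re-imaged, and those who stop without further imaging. A clinically stable subject who progresses at Week 8 and is re-imaged 4 to 6 weeks later has two postbaseline scans, and stays in the subgroup as a nonresponder.

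**The case against.** The best defence is that a two-scan view is a reasonable supportive look at adequately assessed subjects. At an immature data cut, an ongoing subject with one scan may have a PR awaiting confirmation and is not yet a settled nonresponse. SAP 9.1.2.1 itself accepts two scans as one route to Stage 1 evaluability. Part of this stands: before follow-up is complete, such a view carries some information. It weakens at the final analysis. The Stage 1 rule also differs in kind, because it admits subjects who discontinued or reached Week 16, whereas the subgroup has only the scan count. The SAP offers no such rationale and places the entry among baseline subgroups.

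It can also be said that the lead-in mentions subject characteristics as well as baseline variables, and that SAP Appendix A lists no table for this subgroup. Both are fair. But a count of postbaseline scans is an outcome of follow-up, not a characteristic of the subject. The appendix describes its list as a guideline, and the text of 7.3.2.1.1 still specifies the analysis.

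Three stronger readings are tempting, and the documents do not support them.

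- *The subgroup rate always exceeds the true response rate.* The algebra bounds it only against the observed full-denominator rate. That rate can fall below the true one by chance, and so can the subgroup rate.
- *All early progressions are deleted.* The repeat-scan rule keeps stable, re-imaged progressors in. This is also why the assumed range for f starts as low as 10%.
- *A failing cohort would be judged against its target rate.* A reader might note that 10/46, the largest failing count in the SCCHN doublet, would appear as 10/28 = 35.7% if 40% were removed, just above p1 = 35%. But the SAP plans no test or threshold in this subgroup. SAP 7.1, 7.3.2.1 and 9.1.2.1 tie the primary rate to the response evaluable population and the futility rule to its own evaluable set.

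**Conclusion.** The line is wrong as written, at low severity. The direction of the bias follows from the SAP's own definitions and needs no outside figure. The increase is strict as soon as there is one confirmed responder and one removed subject. Only the size is uncertain: it depends entirely on the removed share, and the 11% to 67% range is no firmer than the assumed 10% to 40% behind it. No primary estimate, stopping rule or declaration of activity changes. The consequence is a supportive estimate that is biased upward and carries no warning to that effect.

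**What to change.** Delete the entry from the list in SAP 7.3.2.1.1. In its place, for each treatment group and tumor type, report the number of subjects with 0, 1 and 2 or more postbaseline scans, with the reasons for having fewer than two, beside the confirmed response rate on the full response evaluable denominator. This shows how much early loss there was without conditioning on it.

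If the sponsor wants to keep a two-scan view, move it out of the baseline subgroups and label it as selected on post-treatment data and biased upward. Always show it next to the full-denominator rate and the number excluded.

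The cost is a one-line SAP change and a short count table. It needs no new data and no change to sample size or decision rules. What is given up is the limited use of a two-scan view at an immature cut, and the scan counts largely cover that.
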